Describing Balance Function in Patients Post-COVID-19

NCT04914364

Document Date: July 30, 2021

Purpose of the Study

We hypothesize that patients with COVID-19 will have residual balance dysfunction that are more similar to those with neurological dysfunction than respiratory illness.

Background & Significance

People with cardiorespiratory dysfunction specifically chronic obstructive pulmonary disease (COPD) and lung transplantation have postural instability and increased risk of falls compared to age matched controls. People with COPD are 55% more likely to have falls than their non-COPD counterparts. It is speculated that this increase in fall risk is due to muscle weakness, attention and ability to dual task, decline in activity, polyneuropathy, and pain.

Ninety percent of patients with a history of COVID-19 report at least 1 neurological symptom. The neurological symptoms can occur before, during, or after the respiratory symptoms. Neurological symptoms include gustatory and olfactory dysfunction (35-88%), myalgia (19%), headache (15%), altered mental status, confusion or delirium (9%), and dizziness (9%). In an early report from Italy, they describe myopathy and neuropathy in addition to impaired balance and gait. Balance deficits could logically follow many of these neurological signs and symptoms. Although there is anecdotal evidence for imbalance immediately and long after COVID-19, we are unable to find a study that looked at balance quantitatively. Understanding balance dysfunction following COVID-19 can assist medical personnel in directing intervention for gait and balance dysfunction.

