The act of maintaining upright posture or balance depends on both sensory and motor responses. Sensory information from vision, vestibular and somatosensory provide reference about where the body is in space and how it is moving so that appropriate motor responses can be generated. One can hypothesize that in patients with respiratory dysfunction, balance is affected through a lack of oxygen to the muscles making it a motor balance dysfunction. With neurologic dysfunction, difficulties can be seen with both the sensory and motor systems. Our balance outcome measures can differentiate between motor and sensory balance dysfunction. The Timed "Up & Go" is a measure of motor balance while the modified Clinical Test of Sensory Interaction measures the brain's use of visual, vestibular, and somatosensory for balance. We will describe the differences in the results of the TUG and the mCTSIB in patients with COVID-19 with previously documented balance dysfunction in patients with respiratory and neurological dysfunction (from existing literature).

Design & Procedures

Subjects who meet inclusion criteria (see below) will complete informed consent by the PI or one of the sub-investigators.

Subjects will complete the Activities-Specific Balance Confidence (ABC) Scale, provide number of falls in the past year and since hospital admission, and indicate their dizziness level on a 0-10 visual analog scale (VAS) for current, best and worst in the last 24 hours, and provide a description of dizziness (Asked "How would you describe your dizziness?").

HR, RR, BP, and SpO₂ will be measured at rest and after all outcome measures are completed. RPE (0-10 per modified Borg scale) will be measured after each outcome measure. In addition, HR will be measured after each outcome measure. SpO₂ will be continually monitored via pulse oximetry.

Fraction of inspired oxygen (FiO₂) will be titrated per MD orders. If SpO₂ drops below MD-specified parameters, patients will first be given a 3-minute seated rest break. If SpO₂ recovers above MD-specified parameters after rest break, activity will resume. If SpO₂ remains below MD-specified parameters after rest break or continues to drop with activity, FiO₂ will be titrated to maintain SpO₂ within MD-specified parameters.

The Timed “Up & Go” (TUG) and Modified Clinical Test of Sensory Interaction in Balance (mCTSIB) outcome measures will be randomized per Excel’s RAND function and performed in the order assigned.

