During the TUG, subjects will be timed while standing from a standard chair, walking 3 meters at self-selected speed, turning around, walking back, and sitting back down. Subjects will be guarded by a physical therapist while they are walking to prevent falls.

During the mCTSIB, subjects will be timed (for a maximum of 30 seconds) standing on a firm surface, eyes open and eyes closed, then on a foam surface (Airex pad), eyes open and eyes closed. Subjects will have their arms folded across the chest and feet shoulder distance apart. If it is felt by the investigators that the subjects did not perform at their best level, they will be given a second trial. Subjects will be guarded by a physical therapist during balance activities to prevent falls.

Performance on the outcome measures will be recorded on a data sheet and entered into the spreadsheet manually.

Data will be recorded in a password-protected computerized database. Comorbidities and medications will be included from the medical record. Only Duke study personnel will access the medical record. The database will be de-identified before sharing with the co-investigators who are not Duke employees by a Duke employee.

This is a descriptive study and no intervention will be provided. All the examination/outcome measures are standard measures used in physical therapy.

Selection of Subjects

Inclusion Criteria:

- Age > 18 years and < 90 years
- Primary or secondary diagnosis of COVID- 19 during hospitalization and off COVID-19 isolation
- Receiving care in acute inpatient
- Ability to ambulate 20' with or without an assistive device without dropping >10% of resting SpO₂ (determined from existing PT evaluation)
- Ability to stand with no more than contact guard assistance (determined from existing PT evaluation)
- Not requiring use of mechanical ventilation
- Minimum resting SpO₂ of 88% with or without supplemental oxygen
- No neurological or orthopedic dysfunction that would affect balance
- Cognitively intact and able to follow directions and provide consent

Exclusion Criteria:

- History of 2 or more falls in the year prior to COVID-19 diagnosis or history of balance dysfunction

Subject Recruitment and Compensation

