Potential participants will be identified by Duke study personnel using Maestro Care filters (i.e. COVID-19 and active physical therapy consults). Once identified, patients will be screened via chart review to ensure they meet inclusion and exclusion criteria for the study. The treating physical therapist or assigned nurse will approach all patients who meet the inclusion and exclusion criteria to see if they are interested in participating. Additional screening for current resting SpO₂ parameters and number of falls will occur upon approach as this information cannot be obtained via chart review. Consent will be obtained from either the PI or one of the sub-investigators. No compensation will be provided.

No sample size calculations were performed as this is a descriptive study. We plan to approach up to 40 subjects with a goal sample size of around 30-35 to describe balance in COVID-19.

Risk/Benefit Assessment

The study has small risk and no direct patient benefit but has the potential to provide information for patients who may benefit from future interventions aimed at addressing balance deficits in patients with COVID-19. Physical activity is generally considered to be safe for patients with cardiorespiratory conditions, but patients may incur the following risks:

- Risk of falls or musculoskeletal soreness or injury. This is not greater than what is experienced during standard physical therapy treatment. Subjects will be guarded to prevent falls.
- Risk of increased respiratory symptoms but these will be monitored and examination will be discontinued if subjects' SpO₂ drops > 10% of resting SpO₂. Any increased symptoms should be transitory.

Data Analysis & Statistical Considerations

This is a descriptive study so scores on the balance tests will be described by means and standard deviations for each group. Spearman correlation coefficients or linear regression will be used to determine if vital signs influence the balance scores.

Data & Safety Monitoring

The investigators will monitor for adverse events and report as required to the IRB. As there is no increase in risk beyond what is experienced in standard physical therapy intervention, no data monitoring committee will be used.

Duke study personnel who are interacting with patients will follow all Duke COVID-19 policies. Any required PPE will be worn during study visits. Inclusion criteria requires that patients be off isolation prior to approach for the study.

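### The literature comparison behind the hypothesis has no planned measure of difference or uncertainty, and the mCTSIB times capped at 30 s are to be summarised by mean and SD

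*Combined protocol and SAP*

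**What the plan says.** The combined protocol and SAP treats this point in five places.

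- **Purpose of the Study** states a comparative hypothesis: residual balance dysfunction in patients with COVID-19 is "more similar to those with neurological dysfunction than respiratory illness".
- **Background & Significance** says how it will be addressed: "We will describe the differences in the results of the TUG and the mCTSIB in patients with COVID-19" relative to respiratory and neurological populations taken from existing literature. The same paragraph gives the reasoning. Respiratory disease is expected to act on motor balance, while neurological disease can affect both sensory and motor systems. TUG is the motor measure, and the mCTSIB captures the use of visual, vestibular and somatosensory input.
- **Design & Procedures** sets the cap: in the mCTSIB "subjects will be timed (for a maximum of 30 seconds) standing on a firm surface", then on foam, each with eyes open and eyes closed. That makes four conditions.
- **Subject Recruitment and Compensation** gives a goal of around 30-35 patients and says that no sample size calculation was done because the study is descriptive.
- **Data Analysis & Statistical Considerations** has two analysis statements. One is that "scores on the balance tests will be described by means and standard deviations for each group". The other, "Spearman correlation coefficients or linear regression will be used to determine if vital signs influence the balance scores", concerns vital signs and not the literature comparison.

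No section names the reference studies, a measure of difference, an interval, a median or IQR, or the proportion reaching 30 s.

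**The concern.** Two things the study needs in order to speak to its hypothesis are absent from the stated analysis.

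The first is precision. A statement that the cohort resembles one population more than another rests on differences between the cohort and each reference. The SD shows how patients vary, not how well a difference is known. If means are set beside published means without intervals, a reader of the report is not shown whether an apparent resemblance is larger than sampling error in the cohort and in the reference studies.

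The second is the cap. Patients enter only with "Ability to stand with no more than contact guard assistance", and are excluded for "History of 2 or more falls in the year prior to COVID-19 diagnosis or history of balance dysfunction". Some may therefore hold the full 30 s, most plausibly on the firm surface with eyes open. Where many do, the share at the cap is the main feature of the score, and mean and SD do not show it. The mCTSIB carries the sensory half of the protocol's argument, so the loss bears on the hypothesis itself.

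**Working it through.** The plan has no power, alpha or sample size calculation to reproduce. The checks below measure what the stated summaries leave out.

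**1. Precision of one difference from a published mean**

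Inputs: cohort size n = 30 or 35 (Subject Recruitment and Compensation). Reference study size m = 30 or 100, and an SD common to both cohorts, are assumptions, because the document gives neither.

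Formula, in SD units: 95% CI half-width = t(0.975, n+m−2) × √(1/n + 1/m).

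| n | m | t | √(1/n + 1/m) | Half-width (SD) |
|---|---|---|---|---|
| 30 | 30 | 2.002 | 0.2582 | 0.517 |
| 30 | 100 | 1.979 | 0.2082 | 0.412 |
| 35 | 30 | 1.998 | 0.2488 | 0.497 |
| 35 | 100 | 1.978 | 0.1964 | 0.388 |

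An observed difference smaller than about 0.39 to 0.52 SD therefore has a 95% CI that includes zero. For comparison, the half-width for the cohort mean alone is t(0.975, n−1)/√n = 0.373 SD at n = 30 and 0.344 SD at n = 35, so an interval that ignores the reference study's own error would be too narrow.

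**2. Whether mean and SD fix the share at 30 s**

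Take two possible sets of 30 patients on one mCTSIB condition. No distributional model is needed.

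- Set A: 15 patients at 30 s and 15 at 18 s. Mean = (450 + 270)/30 = 24.0 s. Sum of squares = 30 × 6² = 1080. SD = √(1080/29) = 6.10 s.
- Set B: 24 patients at 27 s and 6 at 12 s. Mean = (648 + 72)/30 = 24.0 s. Sum of squares = 24 × 3² + 6 × 12² = 216 + 864 = 1080. SD = √(1080/29) = 6.10 s.

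Mean and SD are identical. In set A 15/30 = 50% are at the cap (exact 95% CI 31% to 69%). In set B 0/30 = 0% are (exact 95% CI 0% to 12%).

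Mean and SD do set an upper limit. With d = 30 − mean, and the SD computed with divisor n, the share at the cap is at most SD²/(SD² + d²). Here the SD is √(1080/30) = 6.0 s and d = 6 s, so the limit is 36/(36 + 36) = 50%. Sets A and B are thus the two ends of what this mean and SD allow. They show what is possible; they do not predict this cohort's result.

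**The case against.** The strongest reply is that this is a declared descriptive study with no intervention, and it promises only to describe differences. Mean, SD and n will be reported, so any reader who has a reference study's SD and n can compute the interval. That largely stands: for the comparison, the gap is one of pre-specification and presentation, not of lost data. But the reader can do this only once the reference studies are identified, and the plan names none. The argument does not reach the cap, because the share at 30 s cannot be derived afterwards from mean and SD.

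A second reply is that a ceiling is not established. This also stands. Eligibility concerns history and basic standing ability, while patients are found through active physical therapy consults, may need contact guard, and face two foam conditions. A reader might infer a severe ceiling effect; the document gives no figure that supports one.

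A third reply is that intervals for sampling error do not account for differences in age or case mix between acute inpatients and published cohorts, and could lend unearned weight to a claim of similarity. This is correct and has to be said beside the intervals. A related point is that differences in means of capped times share the weakness of those means, which is why the share at 30 s should stand next to them.

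A reader might also be tempted to reduce the hypothesis to whether the cohort mean lies nearer one reference mean than the other on a single scale, and to attach an error rate to that ranking. The document supports neither step. It gives no reference means and no reason to expect the cohort to lie between them, so any such rate would depend on a distance chosen by the reviewer. Its own reasoning concerns a profile: motor impairment is expected in both reference groups, and the sensory conditions are meant to separate them.

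**Conclusion.** The point holds as a shortfall in the stated analysis that a cheap addition to the reporting plan would close. The plan states a comparative hypothesis and commits to describing differences, but its analysis section gives no measure of those differences and no uncertainty. For capped times it names summaries that cannot show the share at the cap.

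The size is a 95% CI half-width of about 0.39 to 0.52 SD per difference, assuming reference studies of 30 to 100 patients with a common SD. For the cap, the same mean and SD are compatible with 0% to 50% at 30 s in the worked example; the actual share is unknown.

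A reader might go further and infer that the study will declare resemblance to neurological disease on point estimates, or that it needs a formal test or a larger sample. The text supports neither. It does not say how the conclusion will be drawn, and a descriptive aim requires neither a test nor a power calculation. No figure in the plan is wrong.

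**What to change.** Amend Data Analysis & Statistical Considerations as follows.

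1. Keep mean and SD, which are needed to match published values, and add median and IQR for the balance scores. For each of the four mCTSIB conditions, report the number and proportion holding the full 30 s with an exact 95% CI.
2. Before data lock, list the respiratory and neurological reference studies for TUG and mCTSIB and state how they were chosen.
3. Report each available difference with a 95% CI that includes the reference study's sampling error, wherever that study publishes its SD and n.
4. Interpret the differences as a profile across TUG (motor) and the mCTSIB conditions (sensory), following Background & Significance. State that resemblance to neurological dysfunction will not be concluded from point estimates alone.
5. State that the intervals cover sampling error and not differences in age or case mix between cohorts.

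The cost is SAP wording, a short list of studies and a few hours of analysis, with no new patients, visits or measurements. The downsides are slightly more reporting, gaps where a reference study omits its SD or n, and the possibility that the comparison must be called inconclusive.

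### Vital signs are related to balance scores without age adjustment or any account of oxygen support, so age may confound and SpO2 may, under one mechanism, understate a respiratory link

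*Combined protocol and SAP*

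**What the plan says.** The whole plan for this analysis is one sentence under Data Analysis & Statistical Considerations: "Spearman correlation coefficients or linear regression will be used to determine if vital signs influence the balance scores". No covariate, stratum or predictor time point follows.

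Design & Procedures lists HR, RR, BP and SpO2, which "will be measured at rest and after all outcome measures are completed". It adds: "In addition, HR will be measured after each outcome measure". SpO2 is also monitored continuously. On oxygen, it says that FiO2 "will be titrated per MD orders", and that FiO2 may be adjusted during testing to bring SpO2 back within the ordered limits. The inclusion criteria accept a resting SpO2 of 88% or more on or off supplemental oxygen. Age appears only as an eligibility range, over 18 to under 90. Comorbidities and medications are collected with no stated analysis role. The target is about 30 to 35 subjects.

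The hypothesis, under Purpose of the Study, is "residual balance dysfunction that are more similar to those with neurological dysfunction than respiratory illness". Background & Significance offers two kinds of respiratory route. In respiratory patients, it proposes, "balance is affected through a lack of oxygen to the muscles", a motor effect. For COPD it reports speculation that "this increase in fall risk is due to muscle weakness, attention and ability to dual task, decline in activity, polyneuropathy, and pain".

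**The concern.** Two subjects with the same recorded SpO2 may differ widely in lung impairment if one is on oxygen and the other on room air. Where impairment acts on balance through, say, muscle weakness or reduced activity, a titrated SpO2 need not follow it, and the correlation with balance may come out weaker than the underlying link.

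Age spans some seven decades and may be related both to vital signs and to TUG and mCTSIB times. An unadjusted correlation can then be partly, or wholly, an age effect.

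This is the only stated analysis that links subjects' own oxygenation to their balance, and the plan words it as a test of influence. A weak SpO2 correlation could be taken as support for a more neurological than respiratory picture when it may partly reflect oxygen therapy.

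**Working it through.** The plan states no alpha, power, effect size, oxygen use or age association, so there is no figure to reproduce. Every input below that is not in the protocol is an assumption.

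**1. Oxygen support, first model.** Impairment L ~ N(0,1). Untreated SpO2 = 93 - 4L + N(0,1), capped at 100. The lowest 25, 50 or 75% are on oxygen. Recorded SpO2 on oxygen = max(untreated, a target drawn from 90-94, 92-96 or 91-98), rounded. TUG correlates 0.5 in size with L (other route) or with recorded SpO2 (delivered route). There are 400,000 simulated subjects (300,000 for partial correction). The joint model regresses the rank of TUG on the rank of SpO2 and on/off oxygen.

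| Route | Shortfall corrected | Spearman, recorded SpO2 | Multiple R, SpO2 + on/off oxygen |
|---|---|---|---|
| Other | none (untreated SpO2) | -0.47 | – |
| Other | 50% | -0.47 to -0.44 | 0.44-0.47 |
| Other | 75% | -0.45 to -0.37 | 0.40-0.46 |
| Other | 100% | -0.40 to -0.25 | 0.36-0.45 |
| Delivered | 100% | -0.49 to -0.47 | 0.47-0.49 |

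The loss is conditional on the route, and small at half correction.

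**2. Oxygen support, second model.** Support O = tL + noise (SD 0.2); delivered saturation S = -(L - O) + noise (SD 0.3). Balance depends on L alone, with correlation 0.50. The S-balance correlation is -0.47 at t = 0, -0.41 at 0.5, -0.24 at 0.8 and -0.07 at 0.95. S and O together give R of 0.48-0.49 throughout; support is graded here rather than on/off. If balance depends on S alone, then at t = 0.8 R is 0.23 with or without O. That smaller value is genuine: oxygen has narrowed the spread of the quantity that matters.

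**3. Precision.** 95% CI = tanh(atanh r ± 1.96 × sqrt((1 + r²/2)/(n - 3))). At n = 30:
- r = -0.25: SE = sqrt(1.031/27) = 0.195, CI -0.56 to 0.13.
- r = -0.47: SE = sqrt(1.110/27) = 0.203, CI -0.72 to -0.11.

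The intervals overlap widely, so this study could not by itself tell an attenuated correlation from an unattenuated one.

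**4. Age.** With no true vital-sign effect, spurious r = corr(age, vital sign) × corr(age, balance). The chance of p < 0.05 is 1 - Φ(1.96 - δ) + Φ(-1.96 - δ), with δ = atanh(r) × sqrt(n - 3).

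| Assumed correlations | Spurious r | n = 30 | n = 35 |
|---|---|---|---|
| 0.2, 0.3 | 0.06 | 6.1% | 6.3% |
| 0.3, 0.3 | 0.09 | 7.6% | 8.0% |
| 0.5, 0.5 | 0.25 | 26.4% | 30.4% |
| 0.5, 0.6 | 0.30 | 36.3% | 41.7% |

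For example, at r = 0.25 and n = 30, δ = 0.255 × 5.196 = 1.33. If the two correlations have opposite signs, the spurious r is negative. On ranks, simulation with correlations of 0.3 to 0.5 in size gives 0.08 to 0.23; after age adjustment it is within 0.02 of zero, with a sampling SD of 0.19 against 0.18-0.19 unadjusted.

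**5. Price of adjustment.** The correlation detectable with 80% power is tanh(2.802/sqrt(n - 3 - k)) for k covariates. At n = 30 it is 0.49, 0.50 and 0.51 for k = 0, 1 and 2; at n = 35 it is 0.46, 0.47 and 0.47. A 2-df joint test of SpO2 and oxygen is a different matter. At n = 30 it changes power by -10 to +28 points on the other route (SpO2 alone 26-59%, joint 38-57%) and loses 9-12 points on the delivered route (76-80% to 65-70%).

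**6. Choice of summary.** If age alone drives TUG (r = 0.5), adjusted R² for a model with age, SpO2 and oxygen averages 0.21 at n = 30; the partial version over age averages about 0. Unadjusted, two null terms give an expected partial R² of 2/(n - 2) = 2/28 = 0.07.

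**The case against.** The strongest reply is that the protocol's own mechanism for balance, oxygen supply to the muscles, is the one under which SpO2 is not attenuated. The other routes come from speculation about falls in COPD. The study is descriptive, and its hypothesis is addressed by setting TUG and mCTSIB results against the literature. This stands: the SpO2 concern is conditional and secondary, and no passage says a weak correlation would be used to support the hypothesis.

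It is also fair that SpO2 is one of four vital signs. RR may carry respiratory signal, and the simulations leave it out. Regression would permit covariates, and resting readings are available as predictors. But the plan specifies neither, so both choices stay open until the data are seen.

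The age point is generic, and excluding subjects with earlier falls or balance dysfunction may weaken it. It still applies to an analysis meant to show influence, and adjustment costs little.

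A reader might infer that adding oxygen support would separate a respiratory from a neurological explanation. It would not: oxygen use may mark general illness severity, including neurological involvement. This, with the power loss on the delivered route, is why the oxygen term belongs in a sensitivity analysis.

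**Conclusion.** The concern holds in a limited form. Associations between vital signs and balance are planned with no age adjustment and no account of oxygen support. Confounding by age is possible in either direction. Understatement of a respiratory link by recorded SpO2 is possible only if impairment acts outside delivered saturation, and it is marked only if titration corrects most of the shortfall. The sizes above rest wholly on assumed inputs.

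Two stronger readings are not supported. One is that titration biases the SpO2 result whatever the mechanism; the oxygen-to-muscle route contradicts it. The other is that oxygen support goes unrecorded; the protocol does not list it among the data, but does not say it is omitted. The point affects how a secondary result is read, not the literature comparison. It is worth acting on because the remedy is cheap and oxygen support may be hard to reconstruct later.

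**What to change.** Add to the data analysis section, with a matching field on the data sheet:

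> Oxygen support (room air or on oxygen, with FiO2 or device and flow where known) is recorded with each SpO2 reading. Resting HR, RR, BP and SpO2 are the main predictors; a reading taken after a test does not predict that test's score. Each association is reported as a crude and an age-adjusted partial Spearman correlation with 95% CI. For SpO2, a sensitivity analysis adds on/off oxygen to the age-adjusted model and reports both terms and the partial R² over age alone, adjusted for degrees of freedom. For each mCTSIB condition, the number at the 30-second cap is shown, and correlations are not interpreted where most subjects reach it. Results are exploratory associations, not influence. A weak SpO2 association does not exclude a respiratory contribution, and an association with oxygen use may reflect general illness severity.

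Resting readings are one defensible choice; what matters is naming the choice in advance. The cost is one data-sheet field, a little more analysis, and one or two degrees of freedom at about 30 to 35 subjects. Oxygen management is unchanged.
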